My long-term goal is to promote successful aging among persons with chronic HIV-1 infection by strategies to optimize physical function and minimize disability and frailty. The primary objective of this proposal is to investigate the GH/IGF-I axis as a potential pathway of early functional impairment in persons aging with HIV. My research is anticipated to advance understanding of the mechanisms and interactions of the GH/IGF-I axis in physical function. My central hypothesis is that a phenotype of accelerated functional impairment observed among some persons with HIV infection will be associated with disruption in the GH/IGF-I axis (the somatopause). This hypothesis will be evaluated through the following specific aim:

**Specific Aim 1: Determine the impact of high or moderate intensity combined resistance (REx) and cardiovascular exercise (CEx) on physical function in older HIV+ (n=36) and HIV- (n=36) adults.**

Approach: Previously sedentary older adults (aged 50-75 years) will undergo a 24 week REx + CEx exercise training intervention.

Hypothesis 1a: Both HIV+ and HIV- older adults will have a significant improvement in physical function (chair rise time) with REx + CEx, but HIV+ will have a *lower* increase than HIV- older adults.

Hypothesis 1b: Both HIV+ and HIV- older adults randomized to a high intensity REx + CEx intervention will have greater improvement in physical function than those randomized to the moderate intensity exercise.

Hypothesis 1c: Utilizing established techniques for screening and training, moderate intensity exercise followed by randomization to either continue a moderate- or progress to high- intensity exercise will result in minimal or no adverse events and will result in similar completion rates, with 80% of participants completing the training program.

**Specific Aim 2: Determine the impact of high or moderate intensity combined REx and CEx on local and systemic IGF-I, as an explanatory factor in the physical function changes of older HIV+ and HIV- adults.**

Approach: Previously sedentary older adults (aged 50-75 years) will undergo a 24 week REx + CEx exercise training intervention.

Hypothesis 2a: HIV+ older adults will have lower *systemic* IGF-I at baseline and at week 20 compared to HIV- adults, with blunted response to exercise training.

Hypothesis 2b: HIV+ older adults will have lower baseline and lower week 20 *skeletal muscle* IGF-I mRNA and IGF-I protein, compared to HIV- adults

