Sedentary time and sleep quality will be measured using two tools. Actiwatch Spectrum, accelerometers to collect physical activity and wake/sleep time through additional sensors for light and dark, will be worn for 1 week between the 1st procedure visit and the first exercise visit, and for 1 week between the week 24 and the procedure visit #2.

Accelerometers have been calibrated in [name] laboratory at Rush University, and data will be analyzed in conjunction with her laboratory. We will assess change in sedentary time and change in sleep using the actiwatch. The Pittsburgh sleep index and the Munich Chronotype will assess usual sleep habits and restfulness following sleep.

In addition, each participant will be provided with a pedometer (*Omron Tri-Axis USB Pedometer, HJ-324U*) to wear every day through the study to monitor overall activity patterns and changes with an exercise intervention. This monitor stores 22 days of data. The participant will be asked to bring the monitor every other week and data will be downloaded during the exercise session.

Evaluation of health status, medication use, and falls. A brief health status questionnaire will be completed by participants every 2 weeks to document potential study-related problems/concerns (e.g., exercise discomforts); changes in health status (e.g., hospitalizations), prescription and over-the-counter medications (including non-steroidal anti-inflammatory agents); and falls. The surveys will be reviewed by the study nurse and appropriate follow-up pursued.

Post-intervention follow-up. Participants will be contacted by phone 3 months following study completion. Continued frequency of exercise/physical activity (IPAQ), intent to continue exercising, overall well-being will be assessed.

Risk: A person with a very high depression score may be identified on the CES-D depression screening questionnaire.

Plans to minimize risk: CES-D questionnaires will be briefly reviewed prior to the study participant leaving the visit. If an individual indicates a risk for suicidal ideations or intent on the CES-D, the participant will be referred immediately to their primary care provider or the emergency room.

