## **F. Data Analysis Plan:**

### **Statistical Considerations**

Sample Size Calculations: The primary outcome for sample size calculations is change from baseline in chair rise pace. We assume a change from baseline of 1.5 (SD=1.54) seconds or larger, based on differences observed by fall history [85]: Sample sizes of 36/group will yield an estimate of 29 patients per group at week 16 (~20% dropout). 29 subjects per group achieves over 80% power to detect a between group difference of 1.5 seconds with a significance level of 0.05 and the standard deviation conservatively estimated at 2.0 seconds[110] using a two-sided two-sample equal variance t-test.

Matching and Randomization: Enrollment in the uninfected arm will be constrained to lag behind HIV-enrollments. Upon the enrollment of every 5th HIV-infected patient, HIV-uninfected enrollment will be evaluated and recruiting goals updated to ensure a similar age (<60; >=60), gender, BMI, and smoking

distribution. Given the smaller proportion of women in the HIV-infected population, we plan to enroll fewer women. The randomization will be blocked by gender and exercise intensity to ensure balance according to the following scheme:

Exercise Intensity	Moderate (N=36)		High (N=36)	
HIV-Infected (N=36)	Men:	15	Men:	15
	Women:	3	Women:	3
Controls (N=36)	Men:	15	Men:	15
	Women:	3	Women:	3

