Outcome measures will be available bi-weekly for chair rise, and three times for other functional measures. Serum IGF-I, IGFBP3, muscle IGF-1 mRNA/protein, visceral fat, LBM, and inflammatory cytokines will be measured at procedure visits #1 and #2. Secondary outcomes will include change in other cytokines and hormones, sleep quality, quality of life, V02 peak, strength, and modified SPPB. The inflammatory markers will be tested as mediators on the effect of exercise on changes in function and LBM. Additional secondary outcomes will determine if sedentary time increases as the physical activity intensity decreases, the impact of the intervention on the affect and efficacy of exercise. These factors will be important in design of larger interventions and dissemination to identify points of low exercise efficacy and poor affect and attempt to prevent drop-outs from the intervention. An important outcome is to ensure that intensive 3x/week physical activity does not lead to a decrease in usual activity and an increase in sedentary time due to exercise-related fatigue.

For the inflammatory analyses:

**Analysis.** We propose that no subjects in either arm will experience a major injury (e.g., muscle strain or other injury requiring self-prescribed or provider prescribed treatment) and no more than 1 subject in each group will drop out because of exercise-induced discomfort

(i.e., fatigue, muscle or joint pain). The step counts between arms will be compared to determine if the high-intensity group limits non-study activity. For Aim 3, we will compare the change between arms in IL-6, TNF $\alpha$  and sTNFRI (pre-exercise, and 0, 60, and 90 minutes, and 24 hours) with a single bout of exercise at weeks 2, 12, and 24. We also will compare relative changes in serum IL-6, TNF $\alpha$  and sTNFRI from week 2 to week 24 between groups using geometric means and 95% confidence intervals. Secondary outcomes will include the change in other inflammation (sTNFRII, hsCRP, IL-10) and immune activation (sCD14, sCD163) markers, change in physical function, QoL, depressive symptoms, and exercise self-efficacy between study arms. **Sample size and power.** Sample size calculations were conducted for the within and between group percent change in IL-6, TNF $\alpha$ , hs-CRP, and sTNFRI levels. Data from 49 HIV+ subjects with higher function were used to estimate sample size parameters. We anticipate additional power using

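### Injuries and discomfort drop-outs are judged only by absolute counts, with no interval, no between-arm contrast and no counting window, so the statement says little about relative tolerability of high and moderate intensity

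*Combined protocol and SAP*

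**What the plan says.** Section IV.F, under the inflammatory analyses, expects that "no subjects in either arm will experience a major injury (e.g., muscle strain or other injury requiring self-prescribed or provider prescribed treatment") and that "no more than 1 subject in each group will drop out because of exercise-induced discomfort". The examples given for a major injury therefore include a muscle strain that the participant treats without seeing anyone. No denominator, assumed rate, interval, comparison, time window or consequence is attached to either count.

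Hypothesis 1c (Section I, Specific Aim 1) says that moderate-intensity training followed by randomisation to stay at moderate or progress to high intensity "will result in minimal or no adverse events and will result in similar completion rates, with 80% of participants completing the training program". Section IV.A intends a comparative reading: more drop-outs or poorer compliance with high intensity would count against it.

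Under Section IV.C (Randomization/Week 13 visit), only those still on study at week 13 are randomised. Before that, everyone follows the same low-then-moderate programme (Section IV.D.2). On ascertainment, Section IV.D.8 states: "A brief health status questionnaire will be completed by participants every 2 weeks to document potential study-related problems/concerns". That form also asks about over-the-counter anti-inflammatory drugs.

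**The concern.** Hypothesis 1c and Section IV.A ask how tolerability differs by randomised intensity. A fixed count in each arm is a weak tool for that question. If treated injuries are fairly common, both arms exceed zero whether or not intensity matters. If they are rare, one arm can exceed zero by chance and appear to implicate, or clear, high intensity. If no injury is seen, nothing says how large a rate remains compatible with the data.

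The missing window adds a problem that depends on no assumed rate. An injury in weeks 1-12 cannot have been caused by randomised intensity, yet nothing in the text keeps it out of the count. The definition is broad and the questionnaire is frequent, so minor self-treated strains are likely to be recorded.

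At stake is the injury and discomfort part of the Hypothesis 1c conclusion.

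**Working it through.** **The plan's own figure.** The documents give no operating characteristics for the counts. The only related design calculation is the one that fixes group size. Starting from 36 per group and about 20% dropout, Section IV.F claims that "29 subjects per group achieves over 80% power". Its inputs are a 1.5 s difference, an SD of 2.0 s and a two-sample t-test, two-sided at 5%. Check: 36 × 0.8 = 28.8, or 29. The noncentrality is 1.5 / (2.0 × √(2/29)) = 2.856 on 56 df, which gives power 80.1%. It reproduces.

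**Inputs.** From the documents: 36 per intensity arm (randomisation table, Section IV.F); about 29 after 20% dropout; 13 per group in Table 3 of the inflammatory section. Assumed: a per-person probability p of a treated injury, from 1% to 20%; independence between people; *group* in the drop-out sentence means intensity arm.

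**Zero-injury statement, equal rates.** Per arm, a = 1 − (1 − p)^n. At least one arm fails: 1 − (1 − a)². Both fail: a². Exactly one fails: 2a(1 − a).

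| n per arm | p | a | at least one arm | both arms | exactly one |
|---|---|---|---|---|---|
| 36 | 1% | 30.4% | 52% | 9% | 42% |
| 36 | 2% | 51.7% | 77% | 27% | 50% |
| 36 | 5% | 84.2% | 97.5% | 71% | 27% |
| 36 | 10% | 97.7% | 99.95% | 96% | 4% |
| 29 | 2% | 44.3% | 69% | 20% | 49% |
| 29 | 5% | 77.4% | 95% | 60% | 35% |
| 13 | 2% | 23.1% | 41% | 5% | 36% |
| 13 | 5% | 48.7% | 74% | 24% | 50% |

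At equal 2% rates and 36 per arm, exactly one arm fails in about half of trials. By symmetry, half of those (25% of trials) point at high intensity.

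**Drop-out statement, equal rates, 36 per arm.** An arm fails with two or more discomfort drop-outs: d = 1 − (1 − q)^36 − 36q(1 − q)^35. At q = 2%, d = 16.2%, so at least one arm fails 30% of the time and both 3%. At q = 5%, d = 54.3%, giving 79% and 30%. This limit is less fragile than the zero-injury one.

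**A true difference, 36 per arm, 10% moderate and 20% high.** Moderate arm: 1 − 0.9^36 = 0.9775. High arm: 1 − 0.8^36 = 0.9997. Both fail: 0.977. Only the high arm fails: 0.9997 × 0.0225 = 0.023.

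**What zero events would show.** The exact 97.5% upper limit for 0/n is 1 − 0.025^(1/n): 9.7% for n = 36, 11.9% for n = 29, 24.7% for n = 13.

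**What an estimate would deliver.** The 95% half-width for the risk difference at 10% versus 20%, 36 per arm, is 1.96 × √(0.1×0.9/36 + 0.2×0.8/36) = 0.163, about ±16 points. A test at this size has about 22% power (14% with Fisher's exact test). For 80% power, 199 per arm would be needed.

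**The case against.** The best defence is that the sentence states an expectation, not a decision rule. It is introduced as something proposed, carries no pass/fail label or error rate, and sits in the inflammatory section without naming Hypothesis 1c. That is a fair reading. It does not fill the gap, because injuries and discomfort drop-outs are then left with no stated analysis, while the same paragraph does specify between-arm comparisons for step counts and cytokines.

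A reader might infer three stronger things that the documents do not support:

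- **That almost any realistic injury rate breaks the statement in both arms.** With 36 per arm, both arms fail only 9% of the time at 1% and 27% at 2%. The high figures at those rates (52% and 77%) are for at least one arm. With 13 per arm, all these probabilities are lower. Without an injury rate in the documents, no single range can be chosen.
- **That the counts are the only criterion for Hypothesis 1c.** The hypothesis itself names similar completion and 80% completion. The plan also compares step counts, quality of life, depressive symptoms and exercise self-efficacy between arms, and a safety officer reviews exercise safety every six months.
- **That the count must span 72 people over 24 weeks.** Since arms exist only from week 13, a shorter window and fewer people may be meant. The text does not say, and that ambiguity is part of the point.

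It is also fair that minimal or no adverse events is an absolute claim, which absolute counts partly match, and that a risk difference at this sample size will often be inconclusive. Both objections stand. They support reporting arm-specific proportions alongside the difference, and making no claim of a powered test.

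**Conclusion.** The point holds as a minor one. The plan assesses injuries and discomfort drop-outs by absolute counts alone, without an interval, a between-arm contrast or a stated window. Those counts separate the arms poorly. At treated-injury rates of roughly 6% or more with 36 per arm, both arms fail in at least 80% of trials, even under equal rates. At low equal rates, chance alone often breaks exactly one arm. A clean result leaves a rate near 10% open. The sizes rest on assumed rates, independence and 36 per arm; they shrink with 29 or 13 per arm. The window problem needs none of these assumptions. The statement therefore says little about relative tolerability, although other planned measures address part of that question.

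**What to change.** Keep the expectation if wished, but add an analysis of the events:

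- For injuries and discomfort drop-outs with onset after the week-13 randomisation, report the proportion in each arm with an exact 95% CI, and the high-minus-moderate risk difference with its 95% CI. Label this estimation, not a powered test.
- Tabulate self-treated and provider-treated injuries separately.
- List weeks 1-12 events for the whole cohort, outside the arm comparison.
- State the denominator, and base the injury and discomfort part of the Hypothesis 1c conclusion on these estimates, not on whether the counts were zero and at most one.

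The cost is analysis wording only: the two-weekly questionnaire already covers study-related problems and medication use. The downside is that a yes/no statement becomes a wide interval, often inconclusive.

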**2. Exercise testing and training:** All exercise intervention components will include 3 to 4 weekly, supervised sessions of combined CEx + REx at the University of Colorado-Denver (UCD) Exercise Research Laboratory (ERL). All participants will begin with a 2-week supervised, low-intensity exercise acclimation with an experienced research assistant. The initial goal will be to walk on a treadmill for 20-30 continuous minutes at low-intensity (30-40% of maximal aerobic power [VO2max]) and complete 3 sets of 8 repetitions at low-intensity (40-50% of the one-repetition maximum; 1-RM) 3 or 4 days/week. This will facilitate comfort with study equipment and minimize injury.

At 2 weeks, all participants will complete an additional 10 weeks of moderate- intensity exercise, with a goal of 50 minutes of cardiovascular + 3 sets of 8 resistance exercises by the end of the 12 week initial intervention. This will ensure that every participant meets at least the DHHS-PA recommendations in a supervised setting. At week 13, participants will be randomized to continue moderate intensity exercise, or progress to a high-intensity intervention for an additional 12 weeks.

*Maximal aerobic power (VO2 max).* The measurement of VO2max (or peak) will be used to formulate the prescription for CEx at the screening visit. Increases in VO2max in response to exercise training will also verify that the exercise was of sufficient intensity to induce cardiorespiratory adaptations. During an initial 5-min warm-up, walking speed will be adjusted to elicit a HR that is ~70% of maximal HR (from the screening GXT). Speed will then be held constant and the grade of the treadmill will be increased by 2% every 2 minutes until volitional exhaustion or until the test is stopped (see section 4.1.2b). The O2 and CO2 content of expired air will be measured continuously by open circuit spirometry and averaged every 30 sec using an automated online system (TrueMax 2400; ParvoMedics, Sandy, UT). Objective evidence that VO2max has been attained will include at least 2 of the following: a plateau in VO2 despite an increased energy demand, a respiratory exchange ratio in excess of 1.10, and a maximal HR within 10 beats of the age-predicted value. In the absence of these benchmarks, the maximum measured VO2 will be deemed VO2 peak.

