*Muscle strength (1-RM).* Muscle strength will be evaluated as the 1-RM (the maximal weight that can be lifted only 1 time using correct lifting form through the full range of motion) for the upper and lower body REx performed during weeks 1-20. 1RMs will be measured at week 0 and every 4 weeks to week 20. The change in muscle strength from week 0 to 20 will be a secondary outcome measure.

*Exercise intervention.* CEx duration will be increased to 50 minutes of treadmill walking/jogging and exercise intensity will be gradually increased to either 40-50% VO2max (moderate intensity) or 60-70% VO2max (high intensity). By completing 50 minutes of CEx within the 3 weekly visits, we will ensure that all subjects comply with the DHHS guidelines, regardless of their physical activity outside of the routine visits. REx intensity will increase every 2-3 weeks to a target of 3 sets of 8 repetitions at 60-70% of 1-RM (moderate intensity) or >80% of the 1-RM (high intensity).

*Supervised exercise sessions.* Each session will begin with CEx and proceed to REx. Three sets of resistance exercises will include leg press, knee extension, knee flexion, lunges (forward and side), lateral pulldown, chest press, seated row, and dips on a weight-assisted machine. Weight-stack and free weight equipment will be used. Stretching for 10 minutes will conclude each session. Research assistants will supervise exercise, interact frequently with participants, and encourage feedback regarding any discomforts or undue fatigue experienced during or after the exercise sessions. The individualized exercise prescriptions will be geared toward increasing the exercise stimulus while avoiding unfavorable events.

*Physical activity recommendations outside of supervised sessions.* Each participant will be provided with a pedometer (Omron) and recommendations to achieve at least 5,000 steps/day. Walking paths near the participants' home will be mapped for each participant. Information from the NIH Healthy Aging site (exercises for the older adults, nutrition advice, etc) will be provided to each participant at study entry and tip sheets for ways to decrease sedentary time will be provided. Participants will be encouraged to utilize fitness apps (MyFitnessPal, etc) and each subject will receive instructions to partake in physical activity "most" days of the week, outside of their 3x/week supervised sessions.

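### Step counts meant to show non-study activity would, as the plan is written, include supervised treadmill steps, so the between-arm comparison can mask or distort a change in outside activity

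*Combined protocol and SAP*

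**What the plan says.** The comparison is stated once, in section F (Data Analysis Plan) under the inflammatory analyses: "The step counts between arms will be compared to determine if the high-intensity group limits non-study activity". The quantity of interest is therefore activity outside the study. The same section explains why it matters: "An important outcome is to ensure that intensive 3x/week physical activity does not lead to a decrease in usual activity".

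The measuring device is described in section D.8 (Questionnaires and other assessments). Each participant receives a pedometer "to wear every day through the study to monitor overall activity patterns and changes with an exercise intervention". On data handling, that section says the device stores 22 days of data and adds: "The participant will be asked to bring the monitor every other week and data will be downloaded during the exercise session".

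The training that produces session steps is in section D.2 (Exercise testing and training): "All exercise intervention components will include 3 to 4 weekly, supervised sessions of combined CEx + REx". The cardiovascular part is the same length in both arms: "CEx duration will be increased to 50 minutes of treadmill walking/jogging". The target intensity differs: 40-50% of VO2max in the moderate arm and 60-70% in the high arm. Section D.2 also recommends at least 5,000 steps a day, under its paragraph on activity outside the supervised sessions.

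No section says that the pedometer comes off for sessions, that session steps are subtracted, or that only non-session days are analysed.

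**The concern.** The stated measure does not match the stated question. A device worn every day to capture overall activity records outside steps plus session steps. The question concerns outside steps alone. The session part is delivered under the randomised treatment, so randomisation does not balance it, and any difference between arms in session steps passes straight into the comparison.

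The concern behind the comparison is compensation: people training harder may move less the rest of the time. If the high-intensity arm also takes more steps in its sessions, that surplus offsets the fall the comparison is meant to detect. If it takes fewer, because of missed sessions, the comparison can suggest a fall in outside activity that did not happen. Sections A and G both treat more sedentary time under high intensity as a reason for caution about that regimen, so a misleading step result would feed an interpretation the investigators care about.

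**Working it through.** The plan gives no effect size, SD or power for step counts, so there is no stated figure to reproduce. The check is in two parts: the text, and the possible size.

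**Text.** Purpose (section F): non-study activity. Measure (section D.8): overall activity, every day. Session content (section D.2): treadmill walking or jogging at an arm-specific intensity. Exclusion rule: none found. So, followed literally,

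observed arm difference = true difference in outside steps + difference in session steps.

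**Inputs from the documents:** 50 treadmill minutes per session (the target reached after build-up); 3 to 4 sessions a week; 5,000 steps/day recommended; 36 per intensity arm before dropout.

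**Assumptions (not in the documents):** cadence, step-count SD, size of the outside drop, and a two-sided 5% two-sample t-test.

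**1. Session steps as a share of the total.** At an assumed 100 steps/min, averaged over seven days:
- 3 sessions: 100 × 50 × 3 / 7 = 2,143 steps/day
- 4 sessions: 100 × 50 × 4 / 7 = 2,857 steps/day

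This is not negligible beside 5,000 steps/day.

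**2. Gap from cadence.** Gap = cadence difference × 50 × sessions / 7. At 3 sessions a week:

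| Cadence difference (steps/min) | Gap (steps/day) | Share of 5,000 |
|---|---|---|
| 0 (e.g. intensity raised by grade alone) | 0 | 0% |
| 20 | 429 | 8.6% |
| 25 | 536 | 10.7% |
| 40 | 857 | 17.1% |
| 50 | 1,071 | 21.4% |

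At 4 sessions a week, 50 steps/min gives 50 × 50 × 4 / 7 = 1,429 steps/day.

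**3. Gap from attendance.** With equal cadence of 100 steps/min, one fewer session a week in the high arm lowers its count by 100 × 50 / 7 = 714 steps/day. The two effects can also cancel: the moderate arm at 100 steps/min for 3 sessions takes 100 × 50 × 3 = 15,000 session steps a week, and the high arm at 125 steps/min reaches the same total with 15,000 / (125 × 50) = 2.4 sessions.

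**4. Effect on the comparison.** Suppose outside activity in the high arm truly falls by 1,500 steps/day, with 36 per arm and 3 sessions a week:

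| Session-step gap | Observed difference | Power, SD 2,000 | Power, SD 3,000 |
|---|---|---|---|
| 0 | −1,500 | 88% | 55% |
| 429 | −1,071 | 61% | 32% |
| 857 | −643 | 27% | 15% |

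For a true fall of 1,000 steps/day and a gap of 857, the observed difference is −143 and power is about 6%. These rows show how masking works. They do not predict what this trial will see.

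**The case against.** **Inclusion of session steps is inferred.** The pedometer is issued under advice on activity outside sessions, the comparison is labelled as being about non-study activity, and participants are asked to bring the device in only every other week. A reader could take all this to mean that session steps were never meant to count. That may be the intention, but no wear rule or analysis rule carries it out, and daily wear for overall activity points the other way. It would be too strong to say that contamination is known. What stands is that the plan as written does not prevent it.

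**The direction is not established.** A reader might infer that the comparison must favour the high-intensity arm. The documents do not support that. Both arms share the 50-minute target, intensity is set as a share of VO2max, and no section says whether training intensity is raised by speed or by grade. The two treadmill tests that are described hold speed constant and raise grade, though they are tests and not training, and the training text does allow jogging. Section A itself raises the possibility of lower compliance and more dropout at higher intensity, which would push the gap the other way. Intensity is also raised gradually, so any full gap need not apply throughout weeks 13-24. This objection stands, which is why the range starts at zero.

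**Steps are not the only evidence.** The International Physical Activity Questionnaire (IPAQ) covers activity and sedentary time every four weeks from week 0 to week 24, and the Actiwatch measures sedentary time. A reader might infer that the trial would therefore wrongly rule out compensation on steps alone; that goes too far. But the IPAQ is self-report, the Actiwatch is worn for a week before training and a week after week 24, not during training weeks, and neither is named for this comparison. They support it without repairing it.

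**Conclusion.** The concern holds as a mismatch between measure and question. Under the plan as written, the step comparison would mix outside activity with steps taken under the randomised treatment, and it can mask or distort a change in outside activity. At 3 sessions a week the distortion is 0 to about 1,070 steps/day for an assumed cadence difference of 0 to 50 steps/min. A surplus in the high-intensity arm is plausible but unproven, and lower attendance there would work in the opposite direction. The size rests wholly on assumed cadences, and the inclusion of session steps rests on the daily-wear wording plus the absence of any exclusion. This is a supportive comparison with no stated model, power or decision rule, and the primary chair-rise analysis is untouched. It is a cheap improvement.

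**What to change.** Replace the sentence in section F with a defined comparison: mean daily steps on non-session days during weeks 13-24, compared between intensity arms and adjusted for each participant's mean on non-session days before randomisation. All participants train at the same target intensity before week 13, so that baseline is common to both arms. Add that session dates are to be logged if they are not already; the protocol describes no attendance log. The analysis also needs day-level totals kept at each download.

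For participants still to be trained, an alternative is to have the pedometer taken off during sessions, with the same instruction in both arms. This keeps the rest of the session day in the data. It changes data collection as well as analysis wording, and it cannot be applied to data already gathered.

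Cost: the first option uses 3 to 4 days a week instead of seven, so each participant's mean is less precise. It also misses any drop in activity later on session days, when exercise fatigue might show. For that reason, report IPAQ and Actiwatch sedentary time alongside as supporting evidence, with their limits stated. No new visits or equipment are needed.
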